11.2. Prohibited Medications and Procedures

The use of certain medications, and illicit drugs within 5 half-lives or 28 days, whichever is shorter prior to the first dose of study drug and for the duration of the study will not be allowed. If a prohibited medication is required for single use (such as for a procedure) while study drug is held, the Sponsor-Investigator and Exelixis can approve such use.

The following therapies are prohibited until study treatment has been permanently discontinued:

- Any investigational agent or investigational medical device.
- Oral anticoagulants (e.g., warfarin or other coumarin-related agents, direct thrombin or direct FXa inhibitors, or antiplatelet agents such as clopidogrel, or chronic use of aspirin above low dose levels for cardioprotection per local applicable guidelines).
- Any non-protocol systemic anticancer treatment (e.g., chemotherapy, immunotherapy, radionuclides, drugs or herbal products used specifically for the treatment of the cancer under investigation).

The following therapies should be avoided until study treatment has been permanently discontinued or until otherwise specified:

- Erythropoietic stimulating agents (e.g., epoetin alfa and darbepoetin alfa) should not be used based on a report of increased risk of tumor recurrence/progression associated with erythropoietin.
- Concomitant medications that are known to prolong the QTc interval should be avoided in subjects who receive cabozantinib until they have permanently discontinued cabozantinib treatment (refer to <http://www.qtdrugs.org> for a list of drugs which have the potential to prolong the QTc interval).

- Chronic co-administration of cabozantinib with strong inducers of the CYP3A4 family (e.g., phenytoin, carbamazepine, rifampin, rifabutin, rifapentine, phenobarbital, and St. John's Wort) may significantly decrease cabozantinib concentrations and should be avoided. Selection of alternate concomitant medications with no or minimal CYP3A4 enzyme induction potential is recommended.
- Caution must be used when discontinuing treatment with a strong CYP3A4 inducer in a subject who has been concurrently receiving a stable dose of cabozantinib, as this could significantly increase the exposure to cabozantinib.
- Co-administration of cabozantinib with strong inhibitors of the CYP3A4 family (e.g., boceprevir, conivaptan, posaconazole, ketoconazole, itraconazole, clarithromycin, atazanavir, indinavir, nefazodone, nelfinavir, saquinavir, ritonavir, lopinavir, telaprevir, telithromycin, and voriconazole) may increase cabozantinib concentrations and should be avoided. Grapefruit, star fruit, and Seville oranges may also increase plasma concentrations of cabozantinib and should be avoided.

Additional information on potential drug interactions with cabozantinib is provided in Section 11.3.

11.3. Potential Drug Interactions with Cabozantinib

Cytochrome P450: Data from a clinical drug interaction study (Study XL184-008) show that clinically relevant steady-state concentrations of cabozantinib appear to have no marked effect on the area under the plasma concentration-vs-time curve (AUC) of co-administered rosiglitazone, a CYP2C8 substrate. Therefore, cabozantinib is not anticipated to markedly inhibit CYP2C8 in the clinic, and by inference, is not anticipated to markedly inhibit other CYP450 isozymes that have lower $[I]/[K_i]$ values compared to CYP2C8 (i.e., CYP2C9, CYP2C19, CYP2D6, CYP1A2, and CYP3A4). In vitro data indicate that cabozantinib is unlikely to induce cytochrome P450 enzymes, except for possible induction of CYP1A1 at high cabozantinib concentrations (30 μ M).

Cabozantinib is a CYP3A4 substrate and a weak substrate for CYP2C9 (but not a CYP2D6, CYP2C8, CYP2C19, CYP2B6, or CYP1A2 substrate), based on data from in vitro studies. Results from a clinical pharmacology study, XL184-006, showed that concurrent administration of cabozantinib with the strong CYP3A4 inducer, rifampin, resulted in an approximately 77% reduction in cabozantinib exposure (AUC values) after a single dose of cabozantinib in healthy volunteers. Chronic co-administration of cabozantinib with strong inducers of the CYP3A4 family (e.g., phenytoin, carbamazepine, rifampin, rifabutin, rifapentine, phenobarbital, and St. John's Wort) may significantly decrease cabozantinib concentrations. The chronic use of strong CYP3A4 inducers should be avoided. Other drugs that induce CYP3A4 should be used with caution because these drugs have the potential to decrease exposure (AUC) to cabozantinib. Selection of alternate concomitant medications with no or minimal CYP3A4 enzyme induction potential is recommended.

Results from a clinical pharmacology study, XL184-007, showed that concurrent administration of cabozantinib with the strong CYP3A4 inhibitor, ketoconazole, resulted in a 38% increase in the cabozantinib exposure (AUC values) after a single dose of cabozantinib in healthy volunteers. Co-administration of cabozantinib with strong inhibitors of the CYP3A4 family (e.g., boceprevir, conivaptan, posaconazole, ketoconazole, itraconazole, clarithromycin, atazanavir, indinavir, nefazodone, neflifavir, saquinavir, ritonavir, lopinavir, telaprevir, telithromycin, and voriconazole) may increase cabozantinib concentrations. Grapefruit, star fruit and Seville oranges may also increase plasma concentrations of cabozantinib and should be avoided. Strong CYP3A4 inhibitors should be avoided and other drugs that inhibit CYP3A4 should be used with caution because these drugs have the potential to increase exposure (AUC) to cabozantinib. Selection of alternate concomitant medications with no or minimal CYP3A4 enzyme inhibition potential is recommended.

Please refer to the drug interaction tables at the following websites for lists of substrates, inducers, and inhibitors of selected CYP450 isozyme pathways:

[Http://medicine.iupui.edu/clinpharm/ddis/table.aspx](http://medicine.iupui.edu/clinpharm/ddis/table.aspx)

<http://www.fda.gov/Drugs/DevelopmentApprovalProcess/DevelopmentResources/DrugInteractionsLabeling/ucm080499.htm>.

Protein Binding: Cabozantinib is highly bound ($\geq 99.7\%$) to human plasma proteins. Therefore, highly protein bound drugs should be used with caution with cabozantinib because there is a potential displacement interaction that could increase free concentrations of cabozantinib and/or a co-administered highly protein-bound drug (and a corresponding increase in pharmacologic effect).

Other Interactions: Food may increase exposure levels of cabozantinib by 57%, fasting recommendations should be followed. In vitro data suggest that cabozantinib is unlikely to be a substrate for P-glycoprotein, but it does appear to have the potential to inhibit the P-glycoprotein transport activity. Therefore, cabozantinib may have the potential to increase plasma concentrations of co-administered substrates of P-glycoprotein. Additional details related to these overall conclusions can be found in the investigator brochure.

Administration of the proton pump inhibitor (PPI) esomeprazole resulted in no clinically-relevant effect on cabozantinib plasma PK in healthy volunteers. Therefore, concomitant use of gastric pH modifying agents (i.e., PPIs, H₂ receptor antagonists, and antacids) is not contraindicated in subjects administered cabozantinib.

Additional details regarding potential drug interactions with cabozantinib can be found in the investigator brochure.

Cabozantinib was shown to be a substrate of drug transporter MRP2 in an in vitro assay. Administration of MRP2 inhibitors to subjects may result in increases in cabozantinib plasma concentrations.

12. STATISTICAL CONSIDERATIONS

12.1. Safety Analysis

The safety analysis set includes all treated subjects.

Safety and tolerability will be monitored through continuous reporting of treatment-emergent and TRAEs, AEs of special interest, laboratory abnormalities, and incidence of subjects experiencing dose modifications, dose delay/dose not given, dose interruptions, and/or premature discontinuation of IP due to an AE. All AEs will be recorded by the investigator from the time the subject signs informed consent until 30 days after the last dose of IP. Adverse events will be graded by NCI CTCAE v5.0.

Physical examination, vital signs, laboratory assessments (e.g., serum chemistry, hematology), and ECOG performance status will be monitored. All SAEs (regardless of relationship to IP) will be followed until resolution or sequelae. Local laboratory analysis will be performed as per study schedule.

12.2. Efficacy Analysis

Assessment of the primary efficacy analysis will take place in real time. Based on anticipated accrual of 40 evaluable subjects, if 9 or more have relapsed or died due to any cause (unless clearly documented as unrelated to investigational diagnosis, e.g., car accident) at or before one year after cabozantinib initiation, then the study will be closed to further accrual, and data will simply be collected on the remaining subjects, as specified in the protocol.

12.3. Exploratory Analysis

Appropriate specimens will be collected in anticipation of the exploratory/correlative studies. Analysis will be undertaken once provision for conduct of planned analyses is made.

12.4. Sample Size Considerations

Phase 1: up to 12 subjects to identify the MTD, but the MTD may be reached with as few as 5 subjects.

Phase 2: For sample size determination, we assume the following:

- Null hypothesis: 1-yr relapse-free survival (local and distant) =75%
- Alternative hypothesis: 1-yr relapse-free survival (local and distant) =90%
- Alpha=0.1 (one-sided).
- Beta=0.1 (power=90%)

Total accrual=40 evaluable subjects.

Anticipate accrual of 6 evaluable subjects from phase I component of study. Therefore, 34 evaluable subjects to accrue in phase II portion of study. Subjects who withdraw for reasons other than toxicity during the DLT Period will be determined to be not evaluable and will be replaced.

Subjects are evaluated for efficacy assessment if they receive at least one dose of cabozantinib in combination with neoadjuvant radiation therapy.

Assuming a 10% drop-out/non-evaluable rate, 44 total subjects would be accrued to the efficacy component for the study to yield 40 evaluable subjects.

From the perspective of efficacy, this study is intended as a screening study of activity. Thus, avoiding a type II error (rejecting the proposed regimen as inactive, when it is an active regimen) is a major consideration. This study is not intended to provide definitive evidence of activity. Therefore, a type I error (false positive) is not considered as critical. For these reasons, we have chosen to increase the power of the study to 90% (minimizing type II errors), while relaxing constraints regarding type I. Specifically, we use a one-sided alpha of 0.10 for rejection of the null hypothesis. Use of a one-sided value is justified based on the high efficacy for *local* control of soft tissue sarcoma provided by the combination of surgery and neoadjuvant radiation therapy (~90%). It is not anticipated that distant disease control would be worsened by addition of cabozantinib to neoadjuvant radiation therapy.

An early stopping rule for accrual to the efficacy component of the study is to be undertaken. If 9 (nine) or more evaluable subjects are found to have died or demonstrated disease recurrence at or before 1 (one) year after cabozantinib initiation, then the efficacy component of the study will be discontinued. This assumes of a binomial probability for the primary endpoint, with a target probability of 0.90 for evaluable subjects to be alive and disease-free at one-year after initiation of cabozantinib therapy. When 9 subjects demonstrate failure with respect to the primary endpoint (disease recurrence or death from any cause), then the upper bound of the 95% confidence interval for the binomial probability distribution would no longer encompass the target probability of 0.90 ($31/40=0.775$, 95%CI:0.62-0.89). At this point, the study would be considered negative with respect to the primary endpoint, and further accrual will be discontinued.

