SAMPLE SIZE ESTIMATE	
Phase I/Dose Escalation: Expected 6, but up to 12 subjects to identify the MTD. Subjects enrolled to Phase 1 who withdraw for reasons other than toxicity during the dose-limiting toxicity (DLT) period will be determined to be not evaluable and will be replaced.
 
Phase II/Dose Expansion: 34 additional subjects
 
For sample size determination, we assume the following:
 
Null hypothesis: 1-yr RFS=75%
 
Alternative hypothesis: 1-yr RFS=0.90
 
Alpha=0.1 (one-sided)
 
Beta=0.1 (power=90%)
 
Total accrual=40 evaluable subjects.
 
Anticipate accrual of 6 evaluable subjects from phase I component of study.
 
34 subjects to accrue in phase II portion of study.
 
Assuming 10% non-evaluable rate, 44 subjects would be accrued to the efficacy component of the study to yield 40 evaluable subjects. Subjects enrolled to Phase 2 who withdraw for toxicity during the initial lead-in cycle will be determined to be not evaluable and replaced.

DURATION OF TREATMENT AND STUDY PARTICIPATION	The study is expected to take approximately 36 months from first subject enrolled to last subject follow-up, including approximately 12 months of enrollment period, an estimated 5 months of treatment.

TABLE OF CONTENTS

PROTOCOL SYNOPSIS.....	3
LIST OF ABBREVIATIONS AND DEFINITIONS OF TERMS.....	11
1. INTRODUCTION.....	15
1.1. Soft Tissue Sarcoma.....	15
1.1.1. Epidemiology	15
1.1.2. Standard Treatment	15
1.1.3. Use of radiotherapy in adjuvant and neo-adjuvant therapy.....	16
1.1.4. Use of chemotherapy in adjuvant and neo-adjuvant therapy	17
1.1.5. Use of chemoradiotherapy in adjuvant and neo-adjuvant therapy.....	19
1.2. Cabozantinib Background	22
1.3. Rationale for Combination of Cabozantinib with Radiation Therapy for High-Risk Soft Tissue Sarcoma of the Extremities.....	23
1.4. Rationale for Starting Dose Selection.....	24
2. STUDY OBJECTIVES AND ENDPOINTS	25
2.1. Objectives	25
2.1.1. Primary Objectives.....	25
2.1.2. Secondary Objective(s)	25
2.1.3. Exploratory Objective(s)	25
2.2. Endpoints	25
2.2.1. Primary Endpoints	25
2.2.2. Secondary endpoints	25
2.2.3. Exploratory endpoints	26
3. STUDY DESIGN	27
3.1. Dose-finding Phase 1 Portion of the Study:.....	27
3.2. Dose Expansion Phase 2 Portion of the Study:.....	28
3.3. Study Duration, End of Study, End of Treatment, End of Treatment Visit, Follow-up Period.....	28
4. STUDY POPULATION	30
4.1. Number of Subjects	30
4.2. Inclusion Criteria.....	30

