Follow-up Period	Follow-up period is the on-study time period after the EOT Visit. All subjects that discontinue study drug and have not withdrawn full consent to participate in the study will continue in the follow-up phase for disease recurrence. Follow up will continue approximately every 12 weeks (± 2 weeks), until either one (1) year has elapsed since initiation of cabozantinib therapy (C1D1), death, withdrawal of consent, disease recurrence, or the study closes, whichever is the earliest. This will include a physical exam and imaging assessment. Thereafter, subjects who will be followed every 6 months (+/- 1 month) until 3 years have elapsed since initiation of cabozantinib therapy (C1D1), end-of-study, death, or withdrawal of consent, whichever is earliest. This evaluation may be made by review of publicly available information, record review and/or telephone contact.
Primary Analysis	For this study will occur once all data for primary and secondary endpoints is collected.
Efficacy Analysis Dataset	This includes all subjects treated with at least one dose of cabozantinib at the recommended phase 2 dose, concurrently with neoadjuvant radiation therapy.
Full Analysis Set	All enrolled subjects who receive at least 1 dose of cabozantinib (treated population). Subjects enrolled to Phase 1 who withdraw for reasons other than toxicity during the DLT Period will be considered not evaluable and will be replaced.

Per-protocol Analysis Set	All enrolled subjects who do not have any prospectively defined protocol violations. Subjects enrolled to Phase 1 or Phase 2 who are unable to tolerate cabozantinib monotherapy will not be considered evaluable for the Phase 1 or 2 component of the study and will be replaced. Subjects enrolled to Phase 1 who withdraw for reasons other than toxicity during the DLT Period will be considered not evaluable and will be replaced.
Progression-free survival	The time from the first dose date to the first observation of a disease progression or death due to any cause.
Overall survival	The time from the first dose date to the date of death due to any cause.

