In the dose-finding Phase 1 portion of the study, dose levels of cabozantinib will be tested in cohorts of 3 subjects each using the 3+3 dose-finding design, with the starting dose of 40mg once daily, with potential dose escalation to 60 mg, or de-escalating to 20 mg daily. The daily dose of cabozantinib will not be increased to more than 60 mg per day. The DLT period will include all subjects enrolled to the phase 1 component of the study. The DLT period is defined as beginning on C1D8 and continuing until 28 days after completion of concurrent radiation therapy and cabozantinib. If no dose-limiting toxicity (DLT) is observed at the starting dose in the first 3 subjects, the next dose cohort would enroll subjects at 60 mg. If 1 DLT is observed any dose cohorts in the first 3 subjects, then additional 3 subjects will be enrolled at that dose level. If ≤ 1 of 6 subjects experience a DLT at the starting dose or higher, enrollment would continue to the next higher dose level. The first 3 subjects of each cohort must complete their DLT period prior to expanding the cohort to include additional subjects to ensure a second DLT is not seen in the first 3 subjects. If ≤ 1 of 6 subjects experience a DLT at the starting dose or higher, enrollment would continue to the next higher dose level.

If ≥ 2 subjects experience a DLT at dose level higher than the starting dose, enrollment will be discontinued for that dose cohort and the previous dose level would be declared the maximum

tolerated dose (MTD). If ≥ 2 subjects experience a DLT at the starting dose of 40 mg once daily (and any lower dose level), further enrollment at that dose level will be discontinued and cabozantinib will be reduced to the next planned dose level.

If a subject is considered Not Evaluable due to withdrawal for reasons other than toxicity during the DLT Period, they will be replaced.

The MTD of cabozantinib is the highest dose level at which ≤ 1 of 6 (or 0 out of 3) subjects experienced a DLT, thus a target DLT rate of roughly 17%. It is possible that the MTD is not reached in this study (e.g., if no DLT observed in the first 3 subjects at 60 mg daily). Recommended Phase 2 dose (RP2D) is identified based of the totality of safety and efficacy data. Once the dose-finding portion of the study is concluded and RP2D is identified, subjects receiving a lower dose may be allowed to receive cabozantinib at the RP2D, based on the investigator judgment.

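### The six Phase 1 subjects counted toward the 40 evaluable are the whole expected Phase 1; under 3.2 at most three of six would carry over, so Phase 2 needs about 37 evaluable rather than 34

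*Combined protocol and SAP*

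**What the plan says.** **Counts.** The Synopsis (Sample Size Estimate) sizes all of Phase 1 as "Expected 6, but up to 12 subjects to identify the MTD", then gives "Phase II/Dose Expansion: 34 additional subjects". Section 12.4 makes the same split: "Anticipate accrual of 6 evaluable subjects from phase I component of study. Therefore, 34 evaluable subjects to accrue in phase II portion of study". The Synopsis, 4.1, 12.2 and 12.4 all give 40 evaluable as the total. The Synopsis, 4.1 and 12.4 add 44 accrued, allowing for 10% loss. Section 4.1 describes the 34 as subjects who accrue, whereas 12.4 describes them as evaluable. Sections 4.1 and 12.4 also say that the MTD could be reached with five subjects.

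**Dose-finding.** Section 3.1 uses cohorts of three. If no DLT "is observed at the starting dose in the first 3 subjects, the next dose cohort would enroll subjects at 60 mg". A three-subject cohort can settle the matter: the MTD rule accepts zero DLTs in three, and 3.1 foresees ending without an MTD "if no DLT observed in the first 3 subjects at 60 mg daily".

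**Who counts for efficacy.** There are three statements:
- Definitions of Terms, Efficacy Analysis Dataset: "at least one dose of cabozantinib at the recommended phase 2 dose, concurrently with neoadjuvant radiation therapy".
- Section 3.2: Phase 1 subjects enrolled at the RP2D level who also meet the Phase 2 eligibility criteria.
- Section 12.4: anyone given at least one dose of cabozantinib together with the radiation, with no condition on dose level.

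**The concern.** Six is used for two different quantities: the expected size of Phase 1 over all dose levels, and the number of Phase 1 subjects who join the efficacy analysis. These agree only if every Phase 1 subject counts whatever the dose level, and 3.2 does not allow that. The Phase 2 accrual target then rests on a carry-over that the plan's own expected case does not supply. The differing rules also leave open which Phase 1 subjects enter the primary analysis. Section 12.4 stresses avoiding a type II error, so a shortfall in evaluable subjects would bear on the aim the design puts first.

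**Working it through.** **1. The plan's own figure.** Inputs from 12.4: p0 = 0.75, p1 = 0.90, one-sided alpha 0.10, power 0.90.
- Normal approximation: n = [(1.2816·√(0.75·0.25) + 1.2816·√(0.90·0.10)) / 0.15]² = [(0.5549 + 0.3845) / 0.15]² = 39.2, so 40.
- Exact binomial at n = 40, rejecting at 34 or more relapse-free: alpha 0.0962, power 0.9005.
- Split: 40 − 6 = 34. Accrual: 40 × 1.1 = 44.

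The total of 40 reproduces, and the subtraction is correct. The question is the six.

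**2. How many Phase 1 subjects sit at the selected dose.** Under 3.1 each level ends in one of four ways: 0/3; two or more of 3; 1/3 then cleared at six; 1/3 then not cleared at six. Two levels are visited, giving 4 × 4 = 16 branches with full cohorts. The RP2D is taken here as the MTD or the top level cleared.

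| Phase 1 total | Branches | Number at the selected dose |
|---|---|---|
| 6 | 4 | 3, 3, 3, and 0 (no level tolerated) |
| 9 | 8 | three with 3, three with 6, two with 0 |
| 12 | 4 | three with 6, one with 0 |

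In a six-subject Phase 1 each level tried has three subjects, so the result does not depend on the RP2D being the MTD. Six at one level needs a total of at least nine, or eight if a cohort closes at its second DLT.

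The documents give no DLT rates. For assumed rates between 5% and 33% per level, the selected dose has three subjects with probability about 0.70 to 0.88, and six with probability about 0.12 to 0.26.

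**3. The three rules applied to a six-subject Phase 1.**

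| Rule | Carried over | Phase 2 evaluable needed for 40 |
|---|---|---|
| 3.2 | at most 3 | 37, or more if one of the three fails Phase 2 eligibility |
| Definitions of Terms | 3 where the RP2D is the highest level tried; possibly more if subjects from a higher level are reduced to it during radiation | 37, or fewer if more are carried over |
| 12.4 | 6 | 34 |

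**4. Power if Phase 2 stops at 34 evaluable.** The normal approximation is Φ[(√n·0.15 − 1.2816·√0.1875) / 0.3]. At n = 37 this is Φ[(0.9124 − 0.5549) / 0.3] = 0.883. The exact column uses the smallest boundary with alpha at or below 0.10.

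| Carried over | n | Normal approximation | Exact |
|---|---|---|---|
| 3 | 37 | 0.883 | 0.840 |
| 4 | 38 | 0.891 | 0.825 |
| 5 | 39 | 0.898 | 0.810 |
| 6 | 40 | 0.905 | 0.9005 |

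Exact power falls from n = 37 to n = 39 and then jumps at n = 40, where the boundary first allows six failures instead of five. Most of the exact drop is therefore discreteness.

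**5. The plan's only printed threshold.** Section 12.4 stops accrual at nine failures. At a true 0.90, the chance of eight or fewer is 0.985 with n = 40 and 0.991 with n = 37, so this rule shows no loss. At a true 0.75 the chances are 0.300 and 0.400, so the rule does not stand in for a one-sided 0.10 test.

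**6. Accrual.** With six carried over, 44 − 6 = 38, so 34 cannot be both accrued and evaluable. With three carried over, 44 − 3 = 41 on the plan's own 44, although 41 × 0.9 = 36.9. Dividing instead, 37 / 0.9 = 41.1, so 42.

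**The case against.** **34 is only anticipated, and 40 governs.** This stands. No section tells Phase 2 to stop at 34, and 3.2 and 4.1 replace subjects who withdraw before radiation. It limits the consequence but does not rescue the split: 34 is the only Phase 2 number printed, and it comes from a carry-over that 3.2 would not give in the expected case.

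**Under 12.4's own rule all six count, so 6 + 34 = 40 is consistent.** Taken alone, yes. The defect lies between sections. That rule would bring subjects treated only at other dose levels into the primary analysis, which 3.2 and the Efficacy Analysis Dataset exclude. Even then, six is not assured if Phase 1 can finish with five.

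**Section 3.1 lets lower-dose subjects move up.** It says "subjects receiving a lower dose may be allowed to receive cabozantinib at the RP2D", but only after dose-finding has concluded. The DLT period runs to 28 days after concurrent therapy, so their radiation is over by then and the Efficacy Analysis Dataset's requirement of concurrent treatment fails.

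**Three is not certain.** This stands in part. Section 7.1.2 allows dose reduction at any time. A subject from a higher level reduced to the RP2D during radiation would meet the Efficacy Analysis Dataset definition, though arguably not 3.2. If the RP2D cohort was itself expanded to six, such subjects could take the carry-over above six. In the other direction, 4.2 has an alkaline phosphatase allowance for Phase 1 only, so a subject at the RP2D could fail Phase 2 eligibility and the carry-over could be below three.

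A reader might therefore infer a firm range of 34 to 37, or a ceiling of six carried over. The documents support neither until one definition is chosen.

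**Conclusion.** The printed split does not follow from the plan's expected case. With six subjects in Phase 1 and the rule in 3.2, at most three carry over and Phase 2 needs about 37 evaluable, three more than printed. The figure of 37 assumes full cohorts of three, all three at the RP2D evaluable and eligible for Phase 2, and 3.2 as the governing rule. The root is the three unreconciled statements of who counts.

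A reader might infer that the trial is underpowered, with power of 84%. The documents do not support that. Power is kept if accrual runs to the stated 40 evaluable. Only if Phase 2 stops at 34 with three carried over does n fall to 37, and the loss is then modest: about 0.88 by the normal approximation. The plan prints no success boundary that would make the exact 0.84 its own figure. This is a consistency error in a stated sample-size figure, worth correcting because it drives accrual planning and the make-up of the primary analysis set.

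**What to change.** 1. Use one efficacy-evaluability definition in the Definitions of Terms, 3.2 and 12.4. State whether a subject reduced to the RP2D during radiation counts.
2. In the Synopsis, 4.1 and 12.4, replace 34 with 40 minus the number of evaluable Phase 1 subjects carried over under that definition. Note that this is 37 if three are carried over, the expected six-subject case under 3.2. Label the number as evaluable, and print no range or ceiling for the carry-over.
3. Give the matching accrual: 41 on the plan's own 44, or 42 by dividing 37 by 0.9.
4. Keep 40 evaluable as the governing total. If 34 is kept as a fixed number, restate the power for the resulting n.

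The cost is one shared definition and one planning count in three places. The 40 evaluable, the 44 total, alpha and power do not change. In the expected case, planned Phase 2 accrual becomes 41 or 42, against the 34 printed in 4.1 or the 38 implied by 44 − 6.
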